### 13.3.4 Analysis of Efficacy Endpoints

We will determine the post-therapy, 3-month  $^{18}\text{F}$ -FDG-PET/CT metabolic complete response rate of oral triapine in combination with cisplatin chemoradiation. The mCR rate and the ORR at RP2D will be calculated with corresponding 95% exact confidence interval (CI). The IV triapine version of this regimen has demonstrated a high response rate of  $>90\%$  in patients with stage IB2, II, IIIA, IIIB, and IVA cervical carcinoma. Thus, we could consider the oral treatment not worthy of further study if the response rate is  $<70\%$ . Assuming an inferior margin of 5%, we will conclude that the mCR rate for the study regimen is non-inferior to 70% in this population if we observe at least 23 mCR events in the 28 patients. This is based on a non-inferiority test with type I error of 5%. OS and PFS will be analyzed using the Kaplan-Meier's method. Median survival time will be reported with corresponding 95% CIs.

The proportion of patients experiencing mCR and experiencing objective response will be estimated in both the HIV+ and non-HIV+ cohorts, along with exact 95% binomial confidence intervals. This is an exploratory objective and the trial is not powered for formal statistical tests comparing the cohorts.

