#### 11.1.1 Definitions

Evaluable for toxicity. All patients will be evaluable for toxicity from the time of their first treatment with triapine and cisplatin.

Evaluable for objective response. Only those patients, have received at least 3 cycles of therapy (cisplatin + triapine), and have had their disease re-evaluated (with a 3 month post treatment PET-CT) will be considered evaluable for response. These patients will have their response classified according to the definitions stated below. (Note: Patients who exhibit objective disease progression prior to the end of cycle 1 will also be considered evaluable.)

Evaluable Non-Target Disease Response. Patients who have lesions present at baseline that are evaluable but do not meet the definitions of measurable disease, have received at least one cycle of therapy, and have had their disease re-evaluated will be considered evaluable for non-target disease. The response assessment is based on the presence, absence, or unequivocal progression of the lesions.

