#### 11.1.4.3 Evaluation of 18F-FDG PET CT Target:

**Complete Response (CR):** A metabolic complete response on PET/CT will be defined as greater than -66% reduction in tumor FDG uptake at sites of abnormal tumor FDG uptake noted on pre-treatment FDG-PET study (considering normal cardiac or liver blood pool).

**Partial Response (PR):** A metabolic partial response on PET/CT will be defined as -25% to -66% reduction in tumor FDG uptake at sites of abnormal tumor FDG uptake noted on pre-treatment FDG-PET study (considering normal cardiac or liver blood pool).

**Progressive Disease (PD):** Progressive metabolic disease on PET/CT is classified as an increase in tumor FDG uptake greater than +25% within the tumor region defined on baseline scan (considering normal cardiac or liver blood pool), or appearance of new FDG uptake in new metastatic lesions.

**Stable Disease (SD):** Stable metabolic response will be defined as a change in tumor FDG uptake by less than +25% (increase) or by less than -25% (decrease) at sites of abnormal tumor FDG uptake (considering normal cardiac or liver blood pool) when compared to pre-treatment FDG-PET study.

Patients with a global deterioration of health status requiring discontinuation of treatment or die without objective evidence of disease progression at that time should be reported to be off study treatment due to "symptomatic deterioration." Every effort should be made to document the objective progression even after discontinuation of treatment.

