13.1.1 The RP2D will be determined as described in section 5.1.2. Once the RP2D is determined, two expansion cohorts will be enrolled. Subjects will be enrolled into a non-HIV+ cohort (n=12) to further expand pharmacokinetic investigations and provide additional safety information. Additionally, up to 28 HIV+ cervical cancer patients (including the patients who were treated at the RP2D during the dose escalation stage) will be treated on RP2D to determine whether active HIV antiretroviral therapy impacts the antitumor activity of triapine. A Bayesian continuous monitoring will be used to ensure that the true DLT rate is controlled at 20%. To establish the stopping rule, a week prior distribution of DLT rate is set to be beta ( $\alpha=1, \beta=5$ ). If the posterior probability that the true underlying DLT rate exceeds 20% at RP2D is 70% or higher then the study accrual will be suspended and the toxicity data will be examined by the PI and the research team, who will subsequently decide on whether the trial should be terminated or not.

The enrollment suspension rule using the Bayesian analysis mentioned above can be represented as a table of possible outcomes for DLTs, as shown below.

Bayesian rule for suspending enrollment	
Suspend accrual if n patients experience a DLT	in N patients treated
2	3-4
3	5-8
4	9-13
5	14-17
6	18-22
7	23-26
8	27

The operating characteristics of this study design can be expressed in terms of probability of early suspending the enrollment at RD2P under the assumptions of various the true rates of DLT. The following table calculated these probabilities for a single dose level based on the simulation of 10,000 hypothetical trials.

Frequentist properties of Bayesian rule for suspending enrollment		
Probability of DLT	Probability of suspending	Median sample size for

	the enrollment	each dose level
0.1	0.10	28
0.17	0.32	28
0.2	0.45	28
0.25	0.66	13
0.3	0.83	8

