### 13.3 Data Analysis

#### 13.3.1 Analysis Sets

Evaluable patients: patients who meet all of the protocol inclusion/exclusion criteria and begin treatment with the protocol regimen.

Evaluable patients for DLT: evaluable patients who received at least 80% of the treatment intended during the DLT follow up period as defined in section 5.5 and patients who received any amount of treatment and experienced a protocol defined DLT which leads to the termination of the treatment are evaluable for DLT.

Safety set: data from all evaluable patients who receive initial treatment of the study treatment will be used in the analysis of safety.

Efficacy set: data from all evaluable patients who receive initial treatment of the study treatment will be used in the analysis of efficacy endpoints.

PK and correlative biomarker set: the data from all study-eligible patients (i.e. those meeting all of the protocol inclusion/exclusion criteria) who begin the study treatment and have adequate blood and tissue samples taken will be used in the analyses to address the PK and correlative biomarker aims.

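### The 23-of-28 mCR rule does not name its 28 patients, two sections give conflicting denominators, and a minimum pass excludes 65% rather than the 70% of objective 1.2.1

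*Combined protocol and SAP*

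**What the plan says.** **Objective and endpoint.** Objective 1.2.1 asks whether the 3-month PET/CT mCR rate is 70% or more and mentions no margin. Section 13.1 lists mCR among the secondary efficacy endpoints.

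**Rule.** Section 13.3.4 states that "The mCR rate and the ORR at RP2D will be calculated" with exact 95% confidence intervals. It treats a response rate under 70% as not worth pursuing, takes a 5% margin and a 5% type I error, and will call the regimen "non-inferior to 70% in this population if we observe at least 23 mCR events in the 28 patients". It names neither a cohort nor an analysis set.

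**Candidate groups.** Section 13.1.1 plans "up to 28 HIV+ cervical cancer patients (including the patients who were treated at the RP2D during the dose escalation stage") and 12 non-HIV+ patients. Sections 13.1 and 13.3.5 base the bioavailability precision on 28 patients at the RP2D, with no restriction on HIV status.

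**Denominators.** Under 13.3.1, "data from all evaluable patients who receive initial treatment of the study treatment will be used in the analysis of efficacy endpoints", where evaluable means eligible and started on treatment. Section 11.1.1 is narrower: "Only those patients, have received at least 3 cycles of therapy (cisplatin + triapine") and who "have had their disease re-evaluated (with a 3 month post treatment PET-CT) will be considered evaluable for response", plus those who progress before the end of cycle 1. It adds: "These patients will have their response classified according to the definitions stated below". Those definitions include, in 11.1.4.3, "A metabolic complete response on PET/CT will be defined as greater than -66% reduction in tumor FDG uptake".

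**Replacement.** Section 13.2.1 replaces patients who complete less than 80% of the first cycle without a treatment-ending DLT. It says nothing about a missing 3-month scan.

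**The concern.** This is the plan's only formal efficacy decision rule, and a reader cannot apply it without making three choices.

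- **Which patients are the 28.** The rate is described at the RP2D, the only cohort defined with that number is HIV+, and that cohort is a ceiling that may not fill.
- **Which denominator applies.** Section 11.1.1 removes patients with little treatment or no scan. They are unlikely to be a random subset, so the choice can shift the reported rate.
- **What a pass means.** Objective 1.2.1 speaks of 70% and the rule tests 65%. A pass could be reported as meeting the objective when it does not.

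If these choices are left open, they can be made after the data are seen.

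**Working it through.** **Inputs.** Cutoff 23, n = 28, reference 70%, margin 5%, type I error 5% (13.3.4). Cohorts of up to 28 HIV+ and 12 non-HIV+ (13.1.1). Six evaluable escalation patients at 100 mg, the dose carried forward (5.1.3.6). Formula: P(X ≥ r | n, p) = Σ from k = r to n of C(n,k) p^k (1−p)^(n−k).

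**1. Reproducing the cutoff.** The null is 70% − 5% = 65%. With n = 28, P(X ≥ 22) = 0.0923 and P(X ≥ 23) = 0.0393. The smallest count at or below 0.05 is 23, as stated. Sidedness is not given. A one-sided 2.5% test would need 24 (P = 0.0136), so one-sided 5% is the reading that fits.

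**2. What a pass shows.** The exact one-sided 95% lower bound is the p that solves P(X ≥ r | 28, p) = 0.05.

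| Observed | Rate | One-sided 95% lower bound | Chance of at least this many if true rate is 70% | Same, if true rate is 90% |
|---|---|---|---|---|
| 23/28 | 82.1% | 66.1% | 0.113 | 0.945 |
| 24/28 | 85.7% | 70.2% | 0.047 | 0.858 |

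The minimum pass excludes 65% but not 70%; 24 or more excludes both. The two-sided exact 95% interval at 23/28 is 63.1% to 93.9%, which contains 65%. If the interval planned in 13.3.4 is two-sided, it would sit beside a passed test and appear to contradict it.

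**3. Which group.** RP2D patients could number up to 28 + 12 + 6 = 46. The total is lower if escalation patients count within a cohort or if the HIV+ cohort does not fill. Smallest exact one-sided 5% cutoffs against 65%:

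| n | 24 | 25 | 26 | 27 | 28 | 40 | 46 |
|---|---|---|---|---|---|---|---|
| Cutoff | 20 | 21 | 22 | 23 | 23 | 32 | 36 |

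The number 23 does not carry over. At a true 65%, the chance of 23 or more is 0.876 with n = 40 and 0.988 with n = 46.

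**4. Effect on the reported rate.** Assumed example: 28 treated, 4 unscanned, 20 mCR. Under 11.1.1 the rate is 20/24 = 83.3%. With all treated patients counted and unscanned ones scored as not mCR, it is 20/28 = 71.4%. With the cutoff fixed at 23, both fail.

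**5. Effect on the decision.** Suppose 23 of 28 respond, and one responder was scanned but had fewer than 3 cycles. Counting all treated patients gives 23/28, a pass. Under 11.1.1 it becomes 22/27 = 81.5%, with P(X ≥ 22 | 27, 0.65) = 0.051. That fails both the fixed 23 and the exact cutoff for 27. A group that is not exactly 28 also changes the decision (step 3).

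**The case against.** **The margin is open.** Section 13.3.4 states the 5% margin and words its conclusion as non-inferiority to 70%, so nothing is hidden and 23 is correctly calculated. This stands. What remains is that objective 1.2.1 is worded without the margin.

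**Most passes would exclude 70% anyway.** At a true 90%, 0.858/0.945 = 91% of passes have 24 or more mCR. This also stands. A reader might infer that no pass can support 70%, and that is wrong. The limit concerns what the rule guarantees, which is set by its minimum pass.

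**A fixed 23 already handles missing scans.** A patient without a scan cannot supply an mCR, so the rule in effect treats that patient as a non-event. A reader might infer that dropping unscanned patients turns a fail into a pass, for example 22/28 (p = 0.092) into 22/26 (p = 0.024). That needs a cutoff re-derived for 26, which the plan nowhere provides.

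**The denominator can be read off.** Section 13.1 calls mCR an efficacy endpoint and 13.3.1 assigns efficacy endpoints to all eligible treated patients, while 11.1.1 sits among the RECIST rules. This is a fair reading. But 11.1.1 makes the 3-month PET-CT its condition, and the definitions it points to include the PET category of mCR. Two stated rules conflict and neither yields. The 13.3.1 set also covers every dose level and both cohorts, so it is not a group of 28.

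**The 28 must be the HIV+ cohort.** The number suggests so. Against that, 13.1 and 13.3.5 use 28 without an HIV restriction, the population described just before the rule is defined by stage, and HIV status is an exploratory aim (1.3.1).

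**Conclusion.** The concern holds as an ambiguity about group and denominator, together with a mismatch between an objective and its test. It is not an error in the cutoff.

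The conflict between 11.1.1 and 13.3.1 mainly affects the reported mCR rate and its interval: 12 points in the assumed example (83.3% versus 71.4%). It reaches the decision only if a scanned responder with fewer than 3 cycles is excluded, or if the group is not exactly 28. How often either would occur cannot be judged from the documents.

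On the objective, the minimum pass supports a rate above 65% (lower bound 66.1%), and a regimen with a true rate of exactly 70% passes 11.3% of the time. These figures assume a one-sided exact test, which the plan does not state but which reproduces its cutoff.

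The weight is modest, since mCR is a secondary endpoint in a phase 1 trial. The change is still worth making before the expansion data are read.

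**What to change.** **(a) Group and denominator.** Name the group to which the rule applies, reconciling 13.1.1 with the unrestricted 28 in 13.1 and 13.3.5. Make the mCR denominator all eligible treated patients in that group, and state that the 11.1.1 conditions do not define it.

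**(b) Scoring and size.** Score a missing 3-month PET, early death or progression as not mCR. State how patients replaced for DLT evaluability under 13.2.1 are counted, because counting everyone treated could take the group above 28. Give the exact cutoff against 65% for the group size reached (table in step 3). Report the scanned-only rate as a labelled sensitivity analysis; the IV benchmark in 2.2.1 (23 of 24) also counts only imaged patients.

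**(c) Conclusion.** Keep 23 of 28. Word a pass as an mCR rate exceeding 65% (70% less the 5-point margin), one-sided 5%, and align objective 1.2.1 with that. Report the one-sided 95% lower bound beside the decision, so that a two-sided interval containing 65% does not appear to contradict it.

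**Cost.** Wording only, with no extra patients or scans, and a more limited stated conclusion. Scoring missing scans as not mCR loses power relative to complete scanning. At a true 90% with 10% unscanned (assumed, independent of response), the effective rate is 0.90 × 0.90 = 0.81, and the chance of reaching 23 of 28 falls from 0.945 to 0.554. The loss is smaller if unscanned patients are mostly non-responders. Obtaining the 3-month scans already required by 5.8 limits it.

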### 1.3 Exploratory Endpoints

- 1.3.1 To determine whether active human immunodeficiency virus (HIV) antiretroviral therapy impacts the antitumor activity of triapine.

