## 2.2 CTEP Agent: Triapine

### 2.2.1 IV Triapine

NCI-CTEP has supported a phase I trial (NCI 7336, clinicaltrials.gov NCT00335998) and a phase II trial (NCI 8327, clinicaltrials.gov NCT00941070) evaluating the safety and clinical efficacy of intravenous triapine combined with cisplatin chemoradiation for the management of IB2-IVA cancer of the uterine cervix. Triapine is a 500-to-1000-fold more potent inhibitor of ribonucleotide reductase (RNR) M2 and M2b than hydroxyurea, which has previously shown clinical activity in cervical cancer. The half-life of triapine is approximately 2 hours, suggesting that repeat dosing is needed within one treatment week to optimize clinical efficacy. Cervical cancer cells treated at human pharmacokinetic (PK) concentrations and exposure times survive at a rate of 80% after triapine alone, 40% after triapine plus cisplatin, and 10% after 3-AP plus cisplatin plus radiation. In phase I and II trials, intravenous triapine (25 mg/m^2) was given three times weekly co-administered with weekly cisplatin (40 mg/m^2) and daily radiation (50.4 Gy in 28 fractions) plus brachytherapy (35-40 Gy) in 35 patients with advanced stage cervical and vaginal cancer. This regimen was well-tolerated as a total of 500 (95%) of 525 2-hour 3-AP infusions were administered with the most common side effects being grade 2 diarrhea, grade 2 electrolyte imbalance, grade 2 fatigue, and infrequent grade 3 pancytopenia. In the IV trial (NSC 3663249), 90% of toxicity for this combined regimen occurred within the first 5 weeks of treatment, there is no currently known cumulative risk of toxicity associated with triapine ([name], personal communication). With respect to the secondary objectives of this trial, 3-month metabolic complete responses (mCRs), as determined by PET-CT, were observed in 23 (96%) of 24 patients in whom images were obtained in the phase II study. To date, 29 of 35 (86%) locally advanced cervical cancer patients are alive and disease-free at a median follow-up of 24 months. Four of 35 (11%) patients have died from extra-pelvic disease progression. Based on these findings, a randomized phase II trial of IV triapine in combination with concurrent cisplatin and radiation therapy was initiated (clinicaltrials.gov NCT01835171; Target accrual 188; opened 01/15/2016).

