#### 2.4.2 FDG-PET/CT Imaging as Biomarker of Response

Prior studies have demonstrated that metabolic response can be determined by positron emission tomography (PET) using F-fluorodeoxyglucose (FDG) obtained within 10-16 weeks after the completion of therapy to predict clinical response of cervical cancer. The current recommendations by the National Comprehensive Cancer Network (NCCN) is imaging based on symptoms or suspicious examination findings or a one-time PET-CT at 3-6 months following treatment in LACC can be used to suggest early or asymptomatic persistence/recurrence. This study provides the opportunity to further assess F-FDG-PET/CT metabolic response rate as an early surrogate endpoint in cancer clinical trials.

Complete metabolic response, defined as F-FDG-PET/CT with no evidence of local or distant disease, is approximately 70% after completion of cisplatin-based chemoradiation. Early determination of durable chemoradiation therapy response is an important objective in oncologic care.

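### The exploratory HIV question is analysed by a separate exact interval for each cohort, so no planned output estimates the HIV+ minus non-HIV+ difference or shows how imprecise it is

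*Combined protocol and SAP*

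**What the plan says.** Section 1.3 lists one exploratory aim: "To determine whether active human immunodeficiency virus (HIV) antiretroviral therapy impacts the antitumor activity of triapine". Section 13.1.1 repeats it as the purpose of the HIV+ expansion cohort, which is enrolled "to determine whether active HIV antiretroviral therapy impacts the antitumor activity of triapine".

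The cohort sizes are in the same section: "up to 28 HIV+ cervical cancer patients (including the patients who were treated at the RP2D during the dose escalation stage"), and "Subjects will be enrolled into a non-HIV+ cohort (n=12) to further expand pharmacokinetic investigations".

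The analysis is in Section 13.3.4. The proportions with mCR and with objective response "will be estimated in both the HIV+ and non-HIV+ cohorts, along with exact 95% binomial confidence intervals". The section then adds: "This is an exploratory objective and the trial is not powered for formal statistical tests comparing the cohorts".

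Sections 1.3, 5.4.1, 13.1.1, 13.2.1 and 13.3.4 contain no estimate of the between-cohort difference, no interval for it, no expected half-width and no assumed response rate by HIV status.

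**The concern.** All patients at the recommended phase II dose (RP2D) receive the same regimen, so the only internal evidence on the HIV question is how HIV+ patients compare with non-HIV+ patients. The quantity of interest is a difference, but the plan produces two separate proportions.

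Two 95% intervals side by side are a poor substitute for an interval on the difference, and the exact method with only 12 patients in one cohort makes them wider still. A report could mislead in either direction. Similar rates could be presented as no impact although the data are compatible with a large gap. A sizeable gap could be passed over because the two intervals overlap, although an interval for the difference would exclude zero. The first risk is the greater one in practice, because nothing in the planned output would show the reader how little is known about the contrast.

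**Working it through.** **Inputs**
- Cohort sizes: 28 HIV+ (the stated maximum) and 12 non-HIV+ (Section 13.1.1). That section adds escalation patients only to the HIV+ cohort, so 28 vs 12 is the planned case.
- Reference mCR without triapine: "is approximately 70% after completion of cisplatin-based chemoradiation" (Section 2.4.2).
- mCR with the IV triapine regimen: "were observed in 23 (96%) of 24 patients" (Section 2.2.1).
- Assumption: the documents give no rate by HIV status. If antiretroviral therapy removed the whole benefit of triapine, these two figures would suggest about 70% vs 96%, a gap of 26 points. Other pairs are shown for range.

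**The plan's own figure.** The only mCR design number in Section 13.3.4 is the single-arm cut-off of at least 23 of 28, against 70% with a 5-point margin (null 65%) and 5% type I error. P(X ≥ 23 | 28, 0.65) = 0.039 and P(X ≥ 22 | 28, 0.65) = 0.092, so 23 is the smallest valid cut-off and the figure reproduces. There is no corresponding figure for the HIV contrast.

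**Formulas**
- Cohort intervals: Clopper-Pearson, 95%.
- Difference: d = p1 - p2, with HIV+ as group 1. With Wilson limits (l1, u1) and (l2, u2) for the two proportions, the Newcombe interval is d - √[(p1 - l1)² + (u2 - p2)²] to d + √[(u1 - p1)² + (p2 - l2)²].

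**Step 1: matching rates.** Take 21/28 and 9/12, both 75%. The Wilson limits are 56.6 to 87.3% and 46.8 to 91.1%.
- Lower limit: 0 - √(0.1836² + 0.1611²) = -0.244
- Upper limit: 0 + √(0.1232² + 0.2823²) = +0.308

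Identical observed rates therefore leave about -24 to +31 points open.

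**Step 2: an observed gap.** Take 16/28 and 11/12. The exact intervals are 37 to 76% and 62 to 100%, which overlap. The difference is -35 points, with Newcombe interval -54 to -3.

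**Step 3: all outcomes.** I enumerated every pair (x of 28, y of 12), weighted by the two binomial probabilities.

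| True mCR, HIV+ vs non-HIV+ | Exact intervals separate | Newcombe interval excludes 0 | Mean Newcombe width |
|---|---|---|---|
| 70% vs 96% | 3.0% | 42% | 0.48 |
| 70% vs 90% | 1.4% | 22% | 0.50 |
| 60% vs 90% | 9.4% | 48% | 0.51 |
| 50% vs 90% | 27% | 74% | 0.51 |
| 70% vs 70% | 0.2% | 5.0% | 0.56 |

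Halving the widths gives mean half-widths of about 24 to 28 points. The intervals are asymmetric, as the Step 1 example shows. With no true difference, at 70% in both cohorts, the Newcombe interval excludes zero 5.0% of the time, so its higher rate of excluding zero is not bought with an inflated error rate there.

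**Step 4: sensitivity to cohort size.** Section 5.1.3.6 reports 6 evaluable patients at the dose taken into expansion. If all were non-HIV+ and were pooled with the 12, the comparison would be 28 vs 18. The same enumeration then gives 17% separation against 62% excluding zero at 70% vs 96%, and 46% against 86% at 50% vs 90%. The discrepancy narrows but remains.

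**The case against.** The strongest reply is that the plan promises nothing it fails to deliver. It labels the aim exploratory and says the comparison is unpowered, and two descriptive proportions fit that status. The four counts will be reported, so any reader can compute an interval for the difference. Arguing from how often an interval excludes zero also brings back a test that the plan chose not to make, and the answer depends on the method: for 16/28 vs 11/12, Fisher's exact p is 0.063 although the Newcombe interval excludes zero.

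Much of this stands. A reader might infer that the plan will treat overlapping intervals as evidence of no impact. The documents contain no such rule, so the separation column shows how poorly the side-by-side display reflects the contrast. It is not the error rate of a planned decision. A reader might also take a 40-point gap, such as 50% vs 90%, as the case to plan for. The documents do not support that: their own figures suggest about 26 points, and 50% would place HIV+ patients 20 points below the rate cited for chemoradiation without triapine.

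The cohorts are also not randomised. A difference would mix HIV infection, antiretroviral therapy and case mix, and an interval excluding zero could be over-read as a drug effect. The same limitation applies to side-by-side proportions.

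What the reply does not answer is the omission itself. Lack of power justifies leaving out a p-value. An effect estimate with its interval is the natural descriptive output for an unpowered question, and leaving the reader to derive it makes it likely that the imprecision goes unseen.

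**Conclusion.** The point holds as a modest reporting gap. The plan poses a question that rests on a between-cohort contrast and plans no estimate of that contrast or its precision. At 28 vs 12 the difference would be known to within roughly 24 to 28 points on average over the scenarios examined, and matching rates of 75% would leave about -24 to +31 points open. Under assumed rates of 70% vs 96%, the difference interval excludes zero in about 42% of trials and the separate intervals separate in about 3%.

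These figures assume full cohorts, every patient counted for mCR, and true rates that the documents do not specify by HIV status. The missing contrast is a fact of the text; how readers would interpret two overlapping intervals is an inference. Nothing here shows an undisclosed power failure or an invalid analysis, and neither the sample size nor the primary objectives are affected.

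**What to change.** Add to Section 13.3.4:

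*The difference in mCR and in objective response (HIV+ minus non-HIV+) at the RP2D will be reported with a two-sided 95% Newcombe score interval. It is descriptive and no hypothesis test is made. Because the cohorts are not randomised, it will not be read as the effect of antiretroviral therapy alone.*

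Keep the two cohort-specific exact intervals as supporting output. The cost is one sentence and a line of code, with no change to enrolment, conduct or patient care. The drawback is that the interval will be wide and asymmetric, and some readers may treat it as a test; the last two sentences of the proposed text are there to limit that.
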